Diarrhea/colitis (Grade 1)	Step 1: Treat with antimotility agents (eg, loperamide) and initiate supportive care (see Section 6.5.2). If not improved after 48 hours, treat per guidance for \geq Grade 2.		
Diarrhea/colitis (Grade 2)	Step 1: Interrupt parsaclisib or matching placebo. Perform workup for infection (including CMV, Clostridium difficile , etc) immediately. Initiate or continue supportive care (see Section 6.5.2). Monitor clinical progress closely.		
	Step 2: If improved within 48 hours and/or infection* is confirmed, restart parsaclisib/matching placebo at the same schedule and dose after resolved to ≤ Grade 1 and continue to monitor.		
	*For infectious diarrhea/colitis, follow institutional standard- of-care guidelines and restart parsaclisib/matching placebo according to clinical judgment after resolved to ≤ Grade 1. Consult with medical monitor if needed.		
	Step 3: If not improved within 48 hours and infection is ruled out, start oral steroids or consider IV steroids if participant is being given IV fluids. If no improvement with oral steroids, switch to IV steroids.		
	Step 4: When diarrhea resolves to ≤ Grade 1, continue supportive care and taper steroids according to institutional standard of care. When taper is complete (eg, no steroid or ≤ 10 mg/day prednisone or equivalent) and diarrhea is ≤ Grade 1, restart parsaclisib/matching placebo at the 1 mg QD dose with approval of the medical monitor.		
	Step 5: If Grade 2 diarrhea reoccurs, treat per guidance for diarrhea (≥ Grade 3)/noninfectious colitis.		
	Step 6: If ≥ Grade 2 diarrhea reoccurs a third time, permanently discontinue parsaclisib/matching placebo and the participant will enter the post-treatment follow-up period.		

Table 9: Guidelines for Interruption and Restarting of Study Drug (Continued)

ADVERSE EVENT	ACTION TAKEN
Other toxicities (continued)	
 Diarrhea (≥ Grade 3) Noninfectious colitis (any grade; confirmed or suspected) 	Step 1: Interrupt parsaclisib or matching placebo. Perform workup for infection (including CMV, C. difficile , etc) immediately. Initiate or continue supportive care (see Section 6.5.2). Consider colonoscopy with biopsy for diarrhea ≥ Grade 3 and/or if symptoms suggestive of colitis. Monitor clinical progress closely until resolution.
	Step 2: If infection* is ruled out, start oral steroids or consider IV steroids if participant is being given IV fluids. If no improvement with oral steroids within 48 hours, switch to IV steroids.

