	*For infectious diarrhea/colitis, follow institutional standard- of-care guidelines and restart parsaclisib or matching placebo according to clinical judgment after resolved to ≤ Grade 1. Consult with medical monitor if needed.
	Step 3: When diarrhea/colitis resolves to \leq Grade 1, continue supportive care and taper steroids according to institutional standard of care. When taper is complete (eg, no steroid or \leq 10 mg/day prednisone or equivalent) and diarrhea/colitis is \leq Grade 1, restart parsaclisib or matching placebo at 1 mg QD with approval of the medical monitor. Continue to monitor. If reoccurs, discontinue study drug and the participant will enter the post-treatment follow-up period.
Pneumonitis (Grade 1)	Step 1: Interrupt parsaclisib or matching placebo until the toxicity has resolved.
	Step 2: Restart parsaclisib or matching placebo at the 1 mg QD dose. Monitor as clinically indicated.
Pneumonitis (≥ Grade 2)	Permanently discontinue parsaclisib or matching placebo and the participant will enter the post-treatment follow-up period.
Skin toxicity (eg, rash, pruritus, etc, unless otherwise specified; Grade 2-3)	Step 1: Interrupt parsaclisib or matching placebo until the toxicity has resolved to \leq Grade 1.
	Step 2: Restart parsaclisib or matching placebo at the same dose. If assessed as related to parsaclisib or matching placebo, restart at the 1 mg QD dose.
Exfoliative dermatitis (Grade 1)	Step 1: Interrupt parsaclisib or matching placebo until the toxicity has resolved.
	Step 2: Restart parsaclisib or matching placebo at the 1 mg QD dose. Monitor as clinically indicated.
Exfoliative dermatitis (≥ Grade 2)	Step 1: Interrupt parsaclisib or matching placebo until the toxicity has resolved.
	Step 2: Restart parsaclisib or matching placebo.

Table 9: Guidelines for Interruption and Restarting of Study Drug (Continued)

ADVERSE EVENT	ACTION TAKEN
Other toxicities (continued)	
CMV infection	Participants with CMV viremia without associated clinical signs of CMV infection should be carefully monitored. Consider interrupting parsaclisib or matching placebo for participants with CMV viremia and clinical signs of infection until the infection has resolved. Restart parsaclisib or matching placebo reduce to 1 mg QD dose if approved by the medical monitor.
Varicella zoster infection	Interrupt parsaclisib or matching placebo. Restart parsaclisib or matching placebo only by approval of the medical monitor.

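### Table 9 places Grade 1 and Grade 2 noninfectious colitis under two rows with different actions and does not say which row governs

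*Protocol*

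**What the plan says.** Three rows of Table 9 (protocol Section 6.5.1) deal with diarrhea and colitis.

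- **Grade 1 row.** It is headed "Diarrhea/colitis (Grade 1" and its action is: "Treat with antimotility agents (eg, loperamide) and initiate supportive care (see Section 6.5.2". It has no interruption step. It escalates only on a condition, "If not improved after 48 hours, treat per guidance for" Grade 2 or higher.
- **Grade 2 row.** It covers diarrhea or colitis of Grade 2. Step 1 interrupts study drug and orders an infection work-up. Step 2 reads: "If improved within 48 hours and/or infection* is confirmed, restart parsaclisib/matching placebo at the same schedule and dose", once the event is back to Grade 1 or lower. Step 3 brings in steroids if the event has not improved within 48 hours and infection is excluded. Step 4 then restarts at 1 mg with medical monitor approval. Steps 5 and 6 deal with recurrence and are worded for diarrhea.
- **Any-grade row.** It groups diarrhea of Grade 3 or higher with "Noninfectious colitis (any grade; confirmed or suspected". Step 1 interrupts and works up for infection. Step 2 reads: "If infection* is ruled out, start oral steroids or consider IV steroids if participant is being given IV fluids". Step 3, after the steroid taper, says to "restart parsaclisib or matching placebo at 1 mg QD with approval of the medical monitor", and to discontinue if the event recurs.

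Section 6.5.1 describes the dose-reduction rules as guidelines. Neither the section nor the table ranks one row above another.

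**The concern.** The colitis named in the first two rows is not limited to infectious colitis, and the third row takes in noninfectious colitis of every grade, including suspected cases. A site with a Grade 1 or Grade 2 case can follow the protocol to the letter and arrive at either of two courses of action.

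The stakes are mainly participant safety. Section 2.3 names diarrhea or colitis among the risks for which dose-modification guidance was put in place, and Section 9.6 lists colitis as an event of clinical interest. Discontinuation is affected too. Section 6.5.5 counts the Table 9 discontinuation events as unacceptable toxicity, and Section 7.1.1 says participants with unacceptable toxicity must stop study treatment. Which row a site uses can therefore bear on a mandatory step. It can also feed into the SAP's descriptive tables of adverse events leading to interruption or discontinuation and of daily prednisone use.

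**Working it through.** No arithmetic applies. The check sets the rows side by side for a first episode of noninfectious or suspected colitis.

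| Decision | Grade 1: Grade 1 row | Grade 1: any-grade row | Grade 2: Grade 2 row | Grade 2: any-grade row |
|---|---|---|---|---|
| Interrupt at onset | No such step | Yes | Yes | Yes |
| Infection work-up at onset | No such step | Yes | Yes | Yes |
| Steroids | None before the 48-hour check | Once infection is excluded | Only if not improved at 48 hours and infection excluded | Once infection is excluded |
| Restart dose | No restart needed if never interrupted | 1 mg | Same dose if improved within 48 hours; 1 mg after the steroid branch | 1 mg |
| Medical monitor approval in the row | None stated | Yes | Only for the 1 mg restart | Yes |

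**Grade 1.** The rows differ on every line. The Grade 1 row does not say in words that dosing continues. That follows from the absence of an interruption step, and it holds only until the 48-hour check.

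**Grade 2, not improved at 48 hours, infection excluded.** Both rows lead to steroids and then a 1 mg restart with approval. For a first episode there is no conflict over these actions.

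**Grade 2, improved within 48 hours, noninfectious.** The Grade 2 row restarts at the same dose without steroids. The any-grade row has no improvement branch before steroids, so it leads to steroids and a 1 mg restart with approval. This is the conflict.

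**Infection confirmed.** The event is then no longer noninfectious, and the Grade 2 and any-grade rows carry the same note on infectious cases. The overlap still exists at onset, because the any-grade row applies on suspicion, before the work-up can separate the cases.

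**Recurrence.** The any-grade row discontinues when the event returns after the restart. In the Grade 2 row, a recurrence of Grade 2 diarrhea is sent on to the any-grade row, and permanent discontinuation comes at a third recurrence. These steps speak of diarrhea, so for colitis it is unclear whether they apply. Section 6.5.5 also has its own clause on events that return after reduction to 1 mg, which has to be read together with both rows.

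**Cross-reference.** The Grade 1 row sends unimproved cases to guidance for Grade 2 or higher without naming a row. Grade 2 diarrhea and diarrhea of Grade 3 or higher are in separate rows. This is a minor point. For Grade 1 diarrhea without colitis the Grade 2 row is the natural entry, since neither heading of the later row fits.

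**The case against.** The best defense is that the any-grade row is the more specific one and governs once noninfectious colitis is suspected. The recurrence steps of the Grade 2 row lend some support: they speak only of diarrhea, and Step 5 refers to the later row as the guidance for noninfectious colitis. The reading is not conclusive. It would require colitis in the first two rows to mean infectious colitis only, yet the Grade 1 row has no infection work-up and Step 3 of the Grade 2 row expressly handles cases with infection excluded.

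A second defense is that the rules are guidelines, with sponsor contact on safety concerns, medical monitor consultation before a dose reduction, and consultation recommended before interruption. This softens the conflict and should catch some cases. It does not resolve it, because Sections 6.5.5 and 7.1.1 attach mandatory discontinuation to Table 9.

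A third is that little analysis depends on it. That largely stands. Enrollment is closed, the SAP gives no p-values or treatment comparisons, and its Appendix A lists no dose-reduction table. What remains is guidance to sites for participants still on treatment.

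A reader might infer more than the text supports:

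- **That a Grade 2 participant is kept on drug under one row and interrupted under the other.** Both rows interrupt. The separate row for any Grade 1 or Grade 2 toxicity would, read literally, continue dosing, but it reads as a catch-all and is not relied on here.
- **That the diarrhea rate in Section 2.3 sizes the problem** (22.9% of 35, or 0.229 × 35 ≈ 8). It counts diarrhea of any cause. Diarrhea without confirmed or suspected colitis does not meet two rows, and no colitis rate is given.
- **That an unimproved Grade 1 case sent onward already meets the exit condition of Grade 1 or lower.** The exits also require improvement within 48 hours, confirmed infection or a completed steroid taper.

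**Conclusion.** The inconsistency is real and lies in the wording of Table 9. For a first episode of Grade 1 noninfectious or suspected colitis, the two applicable rows differ on interruption, work-up, steroids, restart dose and approval. For a first Grade 2 episode, the conflict is limited to noninfectious events that improve within 48 hours, where steroids, restart dose and approval differ. The recurrence rules also differ.

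The number of participants affected cannot be worked out from the documents. It is likely to be small: the SAP (Section 1) gives 13 randomized at the termination decision, and protocol Section 2.2 gives 12. The consequence is for the safety of ongoing participants and for consistent handling across sites; the effect on the planned analyses is slight. The conclusion assumes only that the row headings mean what they say and that no precedence rule exists in a document not supplied.

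**What to change.** The sponsor's clinical team should reconcile the diarrhea and colitis rows of Table 9 so that each grade and type of colitis, confirmed or suspected, falls under one row only. The recurrence steps should state whether they apply to colitis and should agree with Section 6.5.5. The Grade 1 row's onward reference should name one row. Which actions apply is for the clinical team to decide.

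The cost is a wording change, by amendment or by letter to sites with ongoing participants. It needs no extra procedures, visits or participants.

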Any Grade 1 or Grade 2 toxicity	Continue study drug administration and treat the toxicity; monitor as clinically indicated.
Any Grade 3 toxicity, if clinically significant and not manageable by	Step 1: Interrupt study drug up to 2 weeks (14 days), until toxicity resolves to ≤ Grade 1.
supportive care	Step 2: Restart study drug at same dose. If assessed as related to study drug, restart study drug at 1 mg QD dose if receiving 2.5 mg and monitor as clinically indicated.
Any recurrent Grade 3 toxicity after dose reduction	Discontinue study drug administration and the participant will enter the post-treatment follow-up period. (Exceptions require approval of sponsor.)
Any other Grade 4 toxicity	Discontinue study drug administration and the participant will enter the post-treatment follow-up period.

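### Protocol Table 9: for exfoliative dermatitis, the Grade ≥ 2 row gives a weaker restart instruction than the Grade 1 row and leaves a 2.5 mg restart open

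*Protocol*

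**What the plan says.** Table 9 (Protocol 6.5.1) has two consecutive rows for this event. Step 1 is the same in both: interrupt until the toxicity has resolved.

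- In the row "Exfoliative dermatitis (Grade 1"), the second step is "Step 2: Restart parsaclisib or matching placebo at the 1 mg QD dose. Monitor as clinically indicated".
- In the row "Exfoliative dermatitis (≥ Grade 2"), the second step is "Step 2: Restart parsaclisib or matching placebo", and the row ends there.

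Other rows of the same table bear on the event:

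- The ordinary skin toxicity row (Grade 2 to 3) yields to any row that specifies otherwise. For a related event it says "If assessed as related to parsaclisib or matching placebo, restart at the 1 mg QD dose".
- The general row "Any Grade 1 or Grade 2 toxicity" says to continue study drug and treat.
- The row beginning "Any Grade 3 toxicity, if clinically significant and not manageable by" supportive care restarts a related event at 1 mg QD. It is followed by "Any recurrent Grade 3 toxicity after dose reduction", for which the action is discontinuation unless the sponsor approves an exception.
- The general Grade 4 row discontinues, but it is worded for Grade 4 toxicities other than those already listed.

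**The concern.** A dose-modification table should become stricter, or at least no looser, as grade rises. Here the mildest form of the event prompts a reduction to 1 mg QD and a reminder to monitor, while every higher grade prompts a bare restart. A site that follows the row as printed could resume 2.5 mg after a Grade 2 event, although a Grade 1 event would have been reduced.

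The stake is participant safety. Protocol 2.3 names severe cutaneous reactions among the drug's risks and relies on the study's dose-modification guidance to manage them. Protocol 9.6 lists exfoliative dermatitis as an event of clinical interest at any grade, whereas rash is listed only from Grade 2. Closing enrollment did not end dosing: under Amendment 2 placebo participants may start parsaclisib early (Protocol 4.1), and the long-term extension is still provided for (Protocol 8.8).

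**Working it through.** No sample size, power or error rate is involved, so the check is a comparison of text.

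**Step 1. Compare events that Table 9 splits by grade.**

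| Event | Lower grade | Higher grade | Direction |
|---|---|---|---|
| AST/ALT | Grade 2: restart at same dose | Grade ≥ 3: restart at 1 mg | stricter |
| ANC/platelets | same dose, then 1 mg on recurrence | same restart steps | level |
| Diarrhea/colitis | Grade 1: supportive care; Grade 2: interrupt | Grade ≥ 3: interrupt, steroids, restart at 1 mg if not infectious | stricter |
| Pneumonitis | Grade 1: interrupt, restart at 1 mg, monitor | Grade ≥ 2: permanent discontinuation | stricter |
| Exfoliative dermatitis | Grade 1: interrupt, restart at 1 mg, monitor | Grade ≥ 2: interrupt, restart | **weaker** |

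Exfoliative dermatitis is the only one of these whose written action weakens with grade. Its Grade 1 steps match those for Grade 1 pneumonitis; the two events part at Grade 2.

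**Step 2. See whether another row closes the gap, grade by grade.**

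- Grade 2: the ordinary skin row gives way because exfoliative dermatitis has its own row. The general Grade 1 or 2 row says to continue. Neither reliably supplies a reduction.
- Grade 3: the general Grade 3 row may apply, but only if the event is clinically significant and not manageable by supportive care. It reduces the dose only if the event is related. The exfoliative dermatitis row does not refer to it.
- Grade 4: the general stop is for other Grade 4 toxicities. Whether it reaches an event that already has a row is ambiguous.

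The gap is therefore clearest at Grade 2.

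**Step 3. Follow a recurrence.**

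- After Grade 1 and a restart at 1 mg: Protocol 6.5.5 counts an AE that recurs after reduction to 1 mg QD as unacceptable toxicity, so the stop is automatic.
- After Grade ≥ 2 and an unreduced restart: that criterion is not met, because there was no reduction. What remains is the 6.5.5 criterion for a related AE judged not to be in the participant's best interest (mandatory once so judged) and the sentence in 6.5.1 that permits discontinuation on recurrence.

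The Grade 1 row states no recurrence rule of its own. It gains one through the dose reduction, and the Grade ≥ 2 row does not.

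**The case against.** The strongest reply is that Table 9 does not stand alone.

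- Protocol 2.2.2 says that participants on 2.5 mg with intolerable AEs should be reduced to 1 mg, and it points to section 6.5.
- Protocol 6.5.1 calls the dose-reduction rules guidelines. It asks for safety concerns to be discussed with the sponsor at once, allows reduction for a related AE or one of unknown relationship, and requires sponsor contact before restart when the delay exceeds 7 days.
- Protocol 6.5.5 makes stopping mandatory on the investigator's or medical monitor's judgment, with or without a prior reduction, and for delays over 21 days unless the sponsor approves longer. Section 7.1.1 adds a stop if participation would be injurious.
- Protocol 9.3 has every AE assessed at each visit until it resolves or is judged permanent, and 2.3 promises close monitoring for toxicities.
- The row requires full resolution, which is stricter than the ordinary skin row's return to Grade 1 or below.

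All of this stands, and it rules out several stronger readings:

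- A reader might infer that the protocol orders a restart at 2.5 mg. It does not; the row is silent on dose.
- A reader might infer that a recurrence after an unreduced restart can meet only a permissive stop. It cannot be put that way, because the judgment-based stop in 6.5.5 is mandatory once invoked.
- A reader might infer that these participants go unmonitored. They do not; the row merely omits words whose substance is in 2.3 and 9.3.
- A reader might take 2.5 mg / 1 mg = 2.5 as a measure of excess risk. It is only the ratio of tablet strengths. The documents give no skin-toxicity rates by dose, and the rise in AE rates reported in 2.2.2 is for oncology doses above 5 mg.

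The reply does not remove the inversion. Each safeguard needs someone's judgment to override the event-specific row, or a delay long enough to trigger contact or a stop. Section 2.2.2 reaches only AEs judged intolerable.

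**Conclusion.** The point holds as a defect in one row. For exfoliative dermatitis the event-specific instruction is weaker at Grade ≥ 2 than at Grade 1, an unreduced restart at 2.5 mg is left open, and such a restart bypasses the automatic recurrence stop. General provisions reduce the risk without correcting the row.

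The size is small in numbers. SAP section 1 reports 13 participants randomized and dosed at the decision to terminate, so at most 13 are affected if none was added later (Protocol 2.2 says 12 randomized). The documents give neither the frequency of exfoliative dermatitis nor the number still on drug, so no event probability can be stated. Efficacy inference is untouched, since SAP section 7 provides no p-values.

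The conclusion assumes that the row is complete as it reads; its sentence is finished and nothing marks a redaction. The sponsor's intent is not documented. A reader might infer from the pneumonitis rows that permanent discontinuation was meant at Grade ≥ 2. The parallel suggests it but does not establish it.

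**What to change.** Amend the Grade ≥ 2 row so that it is no less strict than Grade 1. As a minimum:

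- Grade 2 to 3: interrupt until resolved, restart no higher than 1 mg QD, monitor as clinically indicated, and discontinue on recurrence.
- Grade 4: discontinue permanently.

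Before finalizing, the sponsor should confirm whether permanent discontinuation at Grade ≥ 2, as for pneumonitis, was intended. If so, that stricter rule should be used in place of the minimum.

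The cost is one table row in a protocol amendment, which may need health authority and IRB/IEC approval before use (Protocol 11.1). Data collection and the SAP do not change. The downside is that a few participants may be reduced or stopped who would otherwise have resumed 2.5 mg. If nobody remains on drug in this study, the sponsor should still check whether the row was carried into the rollover study mentioned in Protocol 6.8, whose protocol is not among the documents.

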6.5.2. Supportive Care for Diarrhea/Colitis

Participants should be informed to immediately report to the investigator any event of diarrhea.

Participants should receive appropriate supportive care measures as deemed necessary by the investigator. For any ≥ Grade 1 diarrhea, participants should be advised to drink liberal quantities of clear fluids. If sufficient oral fluid intake is not feasible, fluid and electrolytes should be substituted via IV infusion. Participants should try to eat 5 to 6 small meals per day; low-fat, high-protein foods; and cooked instead of raw vegetables. Participants may supplement their diet with bananas, rice, applesauce, and toast to reduce the number of bowel movements and may also try crackers, gelatin, noodles, or oatmeal. Participants should avoid fried, fatty, greasy, or spicy foods; milk, milk products, and acidic drinks; high-fiber foods and foods that cause gas; and alcohol, caffeine, and herbal supplements (Coutré et al 2015).

For each occurrence, attempts should be made to rule out other causes, such as bacterial or viral infection (including CMV), which might require additional supportive care.

It may be necessary to perform conditional procedures such as colonoscopy with biopsy as part of evaluation of the event. Note that several courses of steroid tapering may be necessary as symptoms may worsen when the steroid dose is decreased.

Participants should be carefully monitored for signs and symptoms of enterocolitis (such as diarrhea, abdominal pain or cramping, blood or mucus in stool, with or without fever) and of bowel perforation (such as peritoneal signs and ileus).

